### ***Disease assessment***

Disease assessment will involve evaluation of leukemic blast proportion in the bone marrow. Hematologic parameters from the routine local assessments including blast percentage (where applicable), absolute neutrophil count (ANC), platelet count, and other relevant parameters such as transfusion dependence will also contribute to this assessment. Evaluation of disease status will be performed at the time-points described in the Schedule of Study Assessment (Table 5). To note, disease assessment must be performed as soon as the peripheral lab results become consistent with an objective response. Disease assessment will also include an aliquot of bone marrow aspirate/biopsy that will be centrally stored for future analysis (e.g. minimal residual disease), if any.

In case bone marrow aspirate/biopsy is consistent with CRi or better response, but still a minimal percentage of peripheral blasts is detected, the response assessment can be postponed up to 2 weeks and will be based on repeated peripheral blood results and last bone marrow aspiration results.

***Transfusion conversion rate and transfusion maintenance rate***

Starting from Protocol V12.0, information about transfusion dependency will be collected and evaluated among study endpoints. For the purpose of defining transfusion conversion rate and transfusion maintenance rate, transfusion status (independent Vs. dependent) at baseline period and post-baseline period are defined as follows for subjects who took at least one dose of study drug:

Baseline transfusion status:

- Baseline period is defined as the period from 28 days prior to the first dose to 28 days post first dose (C2D7). For subjects who are on treatment <28 days, baseline period is from 28 days prior to the first dose (in the event that this information is not available the ICF signature date will be exploited as baseline period start) until the end of treatment.
- Subjects are classified as baseline transfusion independent if there is no red blood cells (RBC) or platelet transfusions within the baseline period; otherwise, the subject is to be considered as baseline transfusion dependent.

Post-baseline transfusion status:

- Post-baseline period is defined as the period from 29 days post first dose (day after C2D7) until last dose.
- For subjects who are on treatment  $\geq 84$  days (C5D1 or more), subjects are classified post-baseline transfusion independent if there is one consecutive 56 days period without any RBC or platelet transfusion in the post-baseline period.
- For subjects who are on treatment  $>28$  days (beyond C2D7) but  $<84$  days (up to C4D21), post-baseline transfusion status is not evaluable.
- Otherwise, the subject is considered post-baseline transfusion dependent.

Both transfusion conversion rate and maintenance rate apply to subjects who have evaluable post-baseline transfusion status.

Transfusion conversion rate is defined as the number of subjects who were transfusion dependent at baseline period but become transfusion independent at post-baseline period divided by the total number of subjects who were transfusion dependent at baseline period. Transfusion maintenance rate is defined as the number of subjects who were transfusion independent at baseline period and still maintain transfusion independent at post-baseline period divided by the total number of subjects who were transfusion independent at baseline period.

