**Figure 1: Cohort expansion and dose escalation plan**

The highest SEL24/MEN1703 dose level considered to be well tolerated and to have optimal PK and PD characteristics, will be called the RD and will be selected for further evaluation in Part 2.

#### 4.2. Part 2

Part 2 is designed to enroll patients at the RD identified in Part 1 based on recommendation by the DMC.

**Part 2** foresees the enrollment of patients to be treated at the RD (identified in Part 1 based on recommendation by the DMC) in the expansion cohorts defined below:

- The expansion cohort in 20 unselected relapsed or refractory AML patients patients (“*all-comers*”)

**NOTE: At the time this protocol version 12.0 is running the expansion cohort in “*all-comers*” AML patients has been already completed with 23 patients enrolled.**

- An additional expansion cohort (“*IDH mutants*”) will enroll approximately 20 relapsed or refractory AML patients harboring an IDH mutation (either IDH1 or IDH2).

The evaluable patients treated at the RD in Part 1 or in Part 2 may be also retrospectively included in exploratory safety/efficacy pooled analysis, including patients with comparable inclusion criteria.

Considering that IDH inhibitors are approved/available only in some of the participating countries, it is anticipated that the study will enroll both IDH inhibitor pre-treated and IDH inhibitor naïve patients. For this reason, the recruitment will aim to have a balanced distribution across the two sub-populations to explore the differences in SEL24/MEN1703 activity between pre-treated and IDH inhibitor naïve patients, if any.

Retrospective correlations between the clinical activity of SEL24/MEN1703 and relevant disease markers (e.g. CD25 expression, FLT3 mutational status, IDH1/IDH2 mutational status, others) may be included in the statistical analysis plan.

Subjects who have a suitable donor and achieve a response allowing them to undergo hematopoietic stem cell transplant (HSCT) per each institution’s assessment can undergo HSCT without leaving the study. However, SEL24/MEN1703 should be stopped and a preHSCT visit should be performed prior to starting the conditioning regimen for HSCT. SEL24/MEN1703 can be resumed after stem cell transplantation if all the following conditions are met:

- Subject is between 30 - 60 days post HSCT

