- Subject has had successful engraftment as demonstrated by absolute neutrophil count (ANC)  $\geq 500/\text{mm}^3$  and platelets  $\geq 20000/\text{mm}^3$  without transfusions
- Subject does not have  $\geq$  grade 2 acute graft-versus-host disease
- Subject is in CR, CRi, CRh

Those subjects resuming treatment will follow the procedures listed under subsequent Cycle 3 Day 1 in the Assessments Schedule. Subjects who do not resume SEL24/MEN1703 will be followed for the applicable endpoints’ assessment.

Finally, MRD status will be recorded immediately prior to the transplant and after the procedure whenever a bone marrow aspirate/biopsy will be collected (recommended every 2 months unless differently indicated by the treating physician based on actual patient’s parameters).

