5.4.2. Secondary endpoints

Study Part 1:

- The number and frequency of AEs, safety laboratory, vital signs and ECG assessments

Study Part 1 and 2:

- Disease assessment will involve evaluation of leukemic blast proportion in the bone marrow. Hematologic parameters from the routine local assessments including blast percentage (where applicable), platelet count, and other relevant parameters such as transfusion dependence will also contribute to this assessment. Disease assessment will also include an aliquot of bone marrow aspirate/biopsy that will be centrally stored for future analysis (e.g. minimal residual disease), if any.
- Overall response rate (ORR), defined as the proportion of patients who have a complete remission (CR), complete remission with incomplete hematologic recovery (CRI), complete remission with partial hematologic recovery (CRh) or morphologic leukemia-free state (MLFS) response to therapy.
- Partial remission (PR) rate, defined as the proportion of patients who have a partial remission response to therapy.
- Duration of response (DoR), defined as the time from the date of first CR, CRI, CRh, CRMRD-, MLFS or PR until the date of documented relapse of any type, progressive disease or death due to disease progression for subjects who achieve CR, CRI, CRh, CRMRD-, MLFS or PR. Subjects who either do not relapse or die without report of relapse are considered nonevents and censored at their last relapse-free disease assessment date. Subjects who undergo an allogeneic HSCT will be considered non events and censored at the time of HSCT

- Relapse free survival (RFS), defined as the time from the date of first CR, CRi, CRh or CRM RD- until the date of documented relapse or death from any cause. Subjects who either do not relapse or do not die are censored at their last relapse-free disease assessment date.
- Event free survival (EFS), defined as the time from the date of first study drug intake until the date of documented relapse, treatment failure or death from any cause. For a subject who did not experience the event, EFS is censored at the date of last relapse-free disease assessment. Subject is not censored at HSCT.
- Overall survival (OS), defined as the number of days between the first study drug administration and death from any cause. Patients without the event are censored at the last date of follow-up.

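### The two transfusion rates have no stop at transplant, so graft-period days count for a patient who resumes drug after HSCT but not for one who does not

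*Protocol*

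**What the plan says.** **Window.** The Protocol synopsis (transfusion conversion and maintenance rates) and Section 5.3.19 use the same definition: "Post-baseline period is defined as the period from 29 days post first dose (day after C2D7) until last dose".

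**Rule inside the window.** For patients on treatment for at least 84 days, "subjects are classified post-baseline transfusion independent if there is one consecutive 56 days period without any RBC or platelet transfusion in the post-baseline period". Patients on treatment for more than 28 but fewer than 84 days are not evaluable. Everyone else is post-baseline dependent.

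**Transplant.** Under Protocol Section 4.2 (repeated in SAP Section 5.1), Part 2 responders with a suitable donor "can undergo HSCT without leaving the study". Drug is stopped before conditioning. Then "SEL24/MEN1703 can be resumed after stem cell transplantation if all the following conditions are met", one of them being "Subject is between 30 - 60 days post HSCT". Another is engraftment, shown by neutrophil and platelet thresholds without transfusion support.

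**SAP.** Section 5.4.2 repeats both rates and limits them to patients with an evaluable post-baseline status. Section 12.1 limits them to the IDH-mutants cohort. Neither mentions HSCT for these rates. For duration of response, Section 5.4.2 does have a rule: "Subjects who undergo an allogeneic HSCT will be considered non events and censored at the time of HSCT". For event-free survival it states the opposite choice, that follow-up continues through HSCT. Section 12.2 plans no subgroup analyses, and no sensitivity analysis sets transplanted patients apart.

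**The concern.** Protocol Table 2 lists both rates under the anti-leukemic activity of SEL24/MEN1703 as a single agent. Once a patient has a donor graft, freedom from transfusion reflects the graft at least in part. Because the window closes at the last dose, resuming drug pulls the transplant, the gap without drug and the engrafted period into it.

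This is not a consistent policy of counting everything that follows treatment. Two patients with the same pre-transplant course are handled differently according to a later decision to resume, and that decision itself depends partly on blood counts held without transfusion. HSCT also has its own rate endpoint, so its benefit could be counted twice. At stake is whether a conversion or maintenance rate in a small cohort can be read as a drug effect.

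**Working it through.** **Convention.** First dose is day 1, as the Protocol's C2D7 label implies: 21 + 7 = day 28.

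**1. The plan's own figure.** 28 on-treatment baseline days + a 56-day run = 84 = 4 × 21. The 84-day limit reproduces, and is the shortest time in which a full run can fit after baseline.

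**2. Days available before transplant.** A run from day 29 ends on day 29 + 56 − 1 = 84. For HSCT on day h, the days from 29 to h − 1 number h − 29, and resumption falls on days h + 30 to h + 60.

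| HSCT day | Post-baseline days before HSCT | Full 56-day run possible? | Resumption days |
|---|---|---|---|
| 50 | 21 | no | 80–110 |
| 64 | 35 | no | 94–124 |
| 84 | 55 | no | 114–144 |
| 85 | 56 | yes | 115–145 |
| 100 | 71 | yes | 130–160 |

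For HSCT before day 85, independence cannot be reached on pre-transplant days alone.

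**3. Direction.** Assumed example: last pre-transplant dose on C2D14 (day 35), HSCT on day 60, last transfusion on day 79.

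- No resumption: the window is days 29–35 (7 days), with 35 days on treatment, so the patient is not evaluable.
- A run from day 80 is complete on day 80 + 56 − 1 = 135. The longest possible run before the day-79 transfusion is days 29–78, or 50 days, which is too short. Dosing must therefore reach day 135.
- Resumption on day 90, last dose after one cycle: 90 + 13 = 103, giving 24 transfusion-free days. After two cycles: 111 + 13 = 124, giving 45 days. A third cycle starts on day 132, so a dose on day 135 completes the run.
- Resumption on day 120, one cycle: last dose on day 133, giving 54 days.

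The documents do not say whether *on treatment* includes the transplant gap. Counted from first to last dose, last doses on days 103, 124 and 133 all pass 84 days without a qualifying run, so the patient becomes dependent: a failure that would not exist without resumption. Counted by cycles given, these patients stay not evaluable until C5D1. With resumption on day 90 as Cycle 3, that is 90 + 42 = day 132. A last dose on day 135 or later then gives a graft-period success on either reading.

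**4. Size.** Let n be the as-written denominator including this patient, and k the number of other independent patients. If the stop makes the patient not evaluable:

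- Graft-period success: (k + 1)/n − k/(n − 1) = (n − 1 − k)/[n(n − 1)], at most 1/n (when k = 0).
- Added failure: k/n − k/(n − 1) = −k/[n(n − 1)], at most 1/n downward (when k = n − 1).

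The documents do not give n. The cohort of about 20 is an upper limit.

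| Assumed n, k | As written, success | As written, failure | With stop |
|---|---|---|---|
| 5, 2 | 3/5 = 60% | 2/5 = 40% | 2/4 = 50% |
| 15, 7 | 8/15 = 53.3% | 7/15 = 46.7% | 7/14 = 50% |

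At k = 0 the shift is 1/n: 5 points at n = 20, 10 at n = 10, 20 at n = 5. For scale, exact 95% intervals are 0.1–24.9% for 1/20 and 0–16.8% for 0/20; 0.5–71.6% for 1/5 and 0–52.2% for 0/5.

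**The case against.** The strongest reply has four parts.

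- **The pathway is narrow.** Section 3.1 requires patients unsuitable for intensive chemotherapy. Section 3.2 excludes systemic immune-modulating therapy for GVHD, and Section 6.9 carries exclusion-criteria prohibitions into the study. Section 6.9.3 bars BCRP inhibitors with study drug, with cyclosporine as an example. Resumption 30 to 60 days after an allogeneic graft may be rare. This stands, and those passages need reconciling with Section 4.2.
- **The SAP has no uniform rule of stopping at HSCT.** Duration of response stops there and event-free survival does not. This stands as a reason to state a choice explicitly. It does not defend a window whose length depends on whether drug is later resumed.
- **The stakes are modest.** The rates are descriptive secondary endpoints in one cohort, and one patient's shift is small beside the exact intervals. This also stands.
- **Resumption does not ensure success.** The engraftment condition applies at the resumption check, sets no duration and does not mention red-cell transfusion, whereas independence needs 56 days without red cells or platelets. A reader might infer that resumers are pre-selected as successes and that the error only inflates the rates. The documents do not support that: short dosing after resumption can produce a failure, as shown above.

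**Conclusion.** The gap is real. As written, post-transplant days count toward a single-agent activity endpoint for patients who resume drug and not for those who do not. For HSCT before day 85, any status of independent depends on those days. Patients transplanted on day 85 or later may already have a full pre-transplant run, so not every resumer is misattributed.

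The bias can go up or down. The upward case needs dosing to continue until a 56-day run is complete. The downward case needs *on treatment* to be counted from first to last dose, which the documents leave undefined. The shift is at most 1/n per affected patient and smaller when the denominator also changes. A reader might infer a fixed gain of 7 to 20 points per patient (1/15 to 1/5), but that holds only if no one else converts and the patient counts as a success.

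The denominators, the number of resumers and the example's transplant and transfusion dates are assumptions; the number of resumers may be zero. The point merits a correction to the definition and does not undermine the study's primary safety aim.

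**What to change.** In the Protocol synopsis, Protocol Section 5.3.19 and SAP Sections 5.4.2 and 12.1, add for transplanted patients:

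- End both the post-baseline window and the time on treatment used for the 84-day rule at the last dose before HSCT conditioning, whether or not drug is resumed. Use the HSCT date if that is the date available.
- Classify those with fewer than 84 days on treatment by then as not evaluable.
- List post-transplant transfusion status separately.
- Report the as-written version as a sensitivity analysis, stating whether the transplant gap counts as time on treatment.

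The cost is one clause and one derived date. Transplant dates are already collected (Protocol synopsis, HSCT rate), and the last earlier dose can be taken from the treatment-intake records (SAP Listing 4.22). A few transplanted patients may become not evaluable and the rates may change slightly. Treatment and visits are unaffected.

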***Allogeneic hematopoietic stem cell transplant (HSCT) rate***

Allogeneic HSCT rate is defined as the percentage of subjects undergoing allo-SCT during the study period. MRD status will be recorded immediately prior to the transplant and after the procedure whenever a bone marrow aspirate/biopsy will be collected (recommended every 2 months unless differently indicated by the treating physician based on actual patient's parameters).

In the event a patient undergoes allogeneic HSCT, the following information will be recorded: a) date of transplant; b) HLA match type (HLA-identical sibling, syngeneic, HLA-matched other relative, HLA-

mismatched relative, Unrelated donor); c) source of stem cells (Bone marrow, peripheral blood, cord blood, others); d) conditioning regimen (myeloablative, non-myeloablative).

### **Pharmacokinetics**

The PK profile of SEL24/MEN1703 and its metabolites (as appropriate) will be evaluated by analysis of concentration levels in plasma. Evaluation of CYP2D6 phenotyping will be carried out. Results will be reported separately. Blood sampling will be performed as described in the Schedule of Study Assessment (Table 5). Left over sample aliquots may be analyzed for metabolite identification purposes. The results of the metabolite identification analysis will be reported separately.

### **Pharmacodynamics**

The PD activity of SEL24/MEN1703 will be assessed by changes between pre- and post-treatment levels of relevant biomarkers e.g. pS6 in peripheral blood by using flow cytometry. Blood sampling for this assessment will be performed as described in the Schedule of Study Assessment (Table 5). Left over sample aliquots may be used for future biomarker analysis which is relevant to the development of SEL24/MEN1703 in AML.

### **Genetic profile of AML cells**

The genetic profile of AML cells of each patient will be performed at the time-points described in the Schedule of Study Assessment (Table 5) by using Next Generation Sequencing and/or qRT-PCR. The mutational status of patients before and after treatment with SEL24/MEN1703 will be assessed by the analysis of a panel of relevant AML mutated genes in bone marrow. Left over sample aliquots and aliquots of bone marrow aspirates/biopsy may be used for future biomarker analysis which is relevant to the development of SEL24/MEN1703 in AML.

### **Statistical Methods:**

This is a preliminary study with a limited number of patients, which is being performed primarily to assess safety. The sample size for this study was determined for both clinical and statistical study design considerations.

Part 1 of the study ran according to the standard “3+3” design. At the 150 mg dose cohort, up to 4 additional patients were to be treated with formulated IMP according to a Bayesian modified toxicity probability interval (mTPI) with a target toxicity rate  $\leq 25\%$ . Safety data have been reviewed prior to progress with additional cohort at higher dose and were to be subject to a protocol amendment.

Part 2 permits further evaluation of the safety and tolerability of the RD of SEL24/MEN1703 in the expansion cohorts defined above.

Statistical analysis will be performed through descriptive statistics only and separately for the two different cohorts (“*all-comers*” and “*IDH-mutant*”).

The evaluable patients treated at the RD in Part 1 or in Part 2 may be also retrospectively included in exploratory safety/efficacy pooled analysis, including patients with comparable inclusion criteria.

On-going safety will be assessed regularly by the DMC during Part 2 and at a minimum when 6 new patients have been dosed (to end Cycle 1) or every 2 months, whichever comes first. No dose escalation steps will be permitted in Part 2.

Demographic data will be displayed, and summary statistics will be used to describe the study population.

Safety data will be tabulated for all patients. Laboratory parameters and adverse events will be included. Adverse events will be tabulated by body system, severity and relation to therapy.

Anti-leukemia activity data will be tabulated.

**Table 5: Schedule of Study Assessments (14 days SEL24/MEN1703 treatment in 21-day cycles)**

Cycle	Screening ≤28-days	Cycle 1							Cycle 2			Cycle 3 onwards		Final Study Visit 	Follow Up 
		D1	D2	D3&4	D7 (±1)	D14 (±1)	D15	D17	D19	D1 (±2)	D7 (±1)	D14 (±1)	D1 (±2)	D14 (±1)	
Demographics	X														
Medical history	X														
Inclusion/exclusion checks	X														
FSH and/or Pregnancy test 	X	X								X			X		X
ECOG PS	X										X			X	X
Vital signs 	X	X									X			X	X
Physical examination 	X	X									X			X	X
Clinical chemistry 	X	X	X	X	X	X				X	X	X	X	X	X
Hematology 	X	X	X	X	X	X				X	X	X	X	X	X
Coagulation 	X	X	X	X	X	X				X	X	X	X		X
Lipid profile 	X	X				X				X		X	X		X
Peripheral blasts 	X	X				X						X		X	X
Urinalysis	X	X									X			X	X
Electrocardiogram 	X	X			X						X			X	X
Echocardiogram (or MUGA scan)	X														
Bone marrow aspirate/biopsy 	X												(X) §		(X)
Disease evaluation 													(X) §		(X)
The genetic profile of AML cells 	X												(X) §		(X)
PD biomarker blood sampling 	X	X				X					X		X	X §	X §
CYP2D6 phenotyping 	X														
CD25 Expression 	X														
Mutational Status 	X														
AML Karyotypic analysis	X														
Adverse events			X	X	X	X					X	X	X	X	X
Concomitant medication	X	X	X	X	X	X					X	X	X	X	X
Transfusion status	X	X	X	X	X	X					X	X	X	X	X
SEL24/MEN1703 administration 		X - once daily dosing for 14 consecutive days in 21-day cycles													
PK sampling (blood) 		X	X		X	X	X	X	X	X	X	X	X	X	
PK (urine collection) 		X	X												
Follow-up assessments															X

**General instructions:**

- Informed Consent must be obtained using the current version of the PIS/ICF prior to commencing Screening.

- On dosing days, assessments should be performed prior to SEL24/MEN1703 dosing unless specified otherwise; tolerance windows for specific assessments are described below.
- (X) denotes an optional sample; please refer to Footnotes.
- X§ denotes a sample not taken at every cycle; please refer to Footnotes.
- Additional assessments may be performed as clinically indicated.

